6. PRIOR AND CONCOMITANT MEDICATIONS

Medications/procedures that start and stop prior to the date of first dose of IMP will be classified as Prior (P) only. If a medication/procedure starts before the date of first dose of IMP and stops on or after the date of first dose of IMP, then the medication/procedure will be classified as both Prior and Concomitant (PC). Medications will be classified as Concomitant (C) only if they have a start date on or after the date of first dose of IMP.

If medication/procedure start and/or stop dates are missing or partial, the dates will be compared as far as possible with the date of first dose of IMP. Medications/procedures will be assumed to be Concomitant only, unless there is clear evidence (through comparison of partial dates) to suggest that the medication/procedure started prior to the first dose of study medication. If there is clear evidence to suggest that the medication/procedure started prior to the first dose of IMP, the medication/procedure will be assumed to be both Prior and Concomitant, unless there is clear evidence to suggest that the medication/procedure stopped prior to the first dose of IMP. If there is clear evidence to suggest that the medication/procedure stopped prior to the first dose of IMP, the medication/procedure will be assumed to be Prior only.

Prior and concomitant medications will be coded according to the World Health Organization Drug Dictionary (WHO-DD) SEP2021 B3 or a later version.

Number and percentage of subjects with prior or concomitant medications will be summarized separately by anatomical therapeutic chemical (ATC) level 3, preferred name (PN) treatment group and overall using PAS. Summaries will be ordered alphabetically for ATC3, and then PN within ATC3.

Prior and concomitant procedures will be coded using the MedDRA 24.0 or a later version. Summaries of prior or concomitant procedures will be ordered alphabetically for SOC, and then PT within SOC.

Summary tables on prior medications/procedures will include "P" only, summary tables on concomitant medications/procedures will include "C" and "PC".

By-subject listings of medications and procedures will be provided, respectively.

7. EFFICACY

7.1 Analysis and Data Conventions

The null hypothesis is that there is no difference between each HMI-115 treatment group and placebo in mean change of DYS measured by NRS from Baseline to Week 12. The alternative hypothesis will be that there is a difference.

All efficacy analyses will be conducted using the PAS. PPS and FAS will be the supplements for partial efficacy analyses. Each comparison will be carried out at the two-sided 5% level of statistical significance unless otherwise specified.

7.1.1 Multi-center Studies

For the summaries and analyses, the term 'Center' will be used to define each investigator site. This study will be conducted by multiple investigators in China, USA and European countries. Multi-center will be pooled by region.

For the primary efficacy variable, the statistical model to be used for the estimation of treatment effects will adjust for differences between regions, by including region as a main effect term in the model. Adjustment for region will also be performed, wherever possible, in the analysis of the secondary efficacy variables.

The homogeneity of the treatment effect across centers will be investigated. A descriptive summary of primary efficacy variable by treatment group and center will be provided. The center information will be presented in the listings.

7.1.2 Adjustments for Covariates

The primary efficacy analysis will be adjusted for the following covariates:

- Region (stratification variable): China, the USA and Europe
- Baseline measure of DYS measured by NRS

7.1.3 Handling of Dropout or Missing Data

Missing data will be imputed using the following methods for the efficacy analyses:

Multiple Imputation (MI): Missing mean change in DYS measured by NRS will be imputed using multiple imputation approach under the assumption of missing-at-random (MAR). Details are described in section 7.2.2.

Mixed-Effect Model Repeat Measurement (MMRM): The repeated measures analyses will be conducted using mixed models including measurements of interest at select visits. The mixed model includes baseline efficacy value as continuous covariate, the categorical fixed effects of treatment, the randomization stratification factor of region, visit and treatment-by-visit interaction, and subject as a random effect unless otherwise specified. An unstructured variance covariance matrix will be used, if the model does not converge, variance components will be used. Parameter estimation is based on the assumption of data being missing at random and using the method of restrictive maximum likelihood (REML). The Kenward-Roger approximation will be used to estimate denominator degrees of freedom. Missing data will not be imputed for MMRM analysis.

Last Observation Carried Forward (LOCF): Missing post-baseline data can be imputed using the LOCF. For any missing data in follow-up period, only the available observation in follow-up period can be carried forward.

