9.4.4 Primary Efficacy Endpoints

The primary efficacy endpoint is the mean change of DYS measured by NRS from Baseline to Week 12.

Measurement of Baseline: The baseline measurements will be derived from the last *complete* menstruation cycle during the Screening Period prior to Day 1.It will be designated as the baseline menstrual cycle and is defined as the interval from the first day of the menstruation to the day before the first day of the next menstruation.

Measurement of Week 12: Because the Week 12 (EOT) visit may or may not occur during menstruation, the measurement of Week 12 will be defined by the following 2 approaches, depending on the scenarios. The objective of these approaches is to capture a complete menstrual cycle and designate it as the EOT menstrual cycle.

- If EOT visit occurs during menstruation, the *EOT menstrual cycle* is defined as the interval that begins from the first day after the end of the previous menstruation to the last day of the menstruation during which the EOT visit occurred. It is expected that the end of this menstruation may be days after the EOT visit.
- If EOT visit occurs outside of a menstruation period, the closest menstruation period to the EOT visit will be identified. This menstrual period may be before or after the EOT visit. In either case, the *EOT menstrual cycle* will begin at the end of the menstruation

Version 6.0 64 of 138 April 11, 2024

period *immediately before* the closest menstruation period to the last day of the closest menstruation period.

The mean change will be summarized for each treatment group with point estimate and 95% CI and will be compared for each HMI-115 treatment group to the placebo group using analysis of covariance models (ANCOVA) with treatment, the randomization stratification factor of region as the fixed effects and baseline DYS as covariate. In addition, a mixed-effect model repeated measures (MMRM) method with treatment, the randomization stratification factor of region, and visit as the main effects, and treatment-by-visit interaction will be used as a sensitivity analysis.

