9.4 EHP-5

The EHP-5 is a valid instrument to measure health-related quality of life in endometriosis. The EHP-5 consists of two parts:

- The core instruments have five scale scores covering:
 - Pain (Found it difficult to walk because of the pain?),
 - Control and powerlessness (Felt as though your symptoms are ruling your life?),
 - Emotional well-being (Had mood swings?),
 - Lack of social support (Felt others do not understand what you are going through?),
 - Self-image (Felt your appearance has been affected?)
- A modular questionnaire consisting of six additional questions:
 - Work (Been unable to carry out duties at work because of the pain?),
 - Relationship with child/children (Found it difficult to look after your child/children?),
 - Sexual intercourse (Felt worried about having intercourse because of the pain?),

- Feelings about the medical profession (Felt the doctor(s) think it is all in your mind?),
- Feelings about treatment (Felt frustrated because treatment is not working?),
- Worries about infertility (Felt depressed at the possibility of not having children/more children?).

Each item is rated on a 4-point scale (never = 0, rarely = 1, sometimes = 2, often = 3, always = 4). Scores on the EHP-5 core and modular questionnaire then are standardized on a scale of 0 (indicating best health status) to 100 (indicating worst health status). If the 'Not Relevant' box was ticked for items on modular questionnaire the score could not be computed for that dimension. After standardization, each item will be scored as (never = 0, rarely = 25, sometimes = 50, often = 75, always = 100).

EHP-5 data (absolute standardized score and CFB) will be summarized descriptively for treatment group at each visit including Baseline (collected on Day 1 before 1st dose of IMP), Week 5, Week 9, Week 13 and Week 25. A negative CFB score indicates improvement in quality of life. CFB will be compared using the MMRM and ANCOVA methods as used for the primary endpoint for each item individually. Missing data will be imputed using LOCF for ANCOVA model.

EHP-5 data will be listed by subject and visit.

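### The SAP's MMRM pairs a random subject effect with an unstructured matrix it does not place, and its only fallback, variance components, can give wrong standard errors for the exploratory EHP-5 analyses

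*SAP*

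**What the plan says.** SAP 7.1.3 gives the only full MMRM specification in the two documents. The fixed part has the baseline value, treatment, region, "visit and treatment-by-visit interaction, and subject as a random effect unless otherwise specified". On covariance it says: "An unstructured variance covariance matrix will be used, if the model does not converge, variance components will be used". Estimation is by restricted maximum likelihood, without imputation. The stated basis is "Parameter estimation is based on the assumption of data being missing at random", and "The Kenward-Roger approximation will be used to estimate denominator degrees of freedom".

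Two things are left open: whether unstructured describes the residual (within-subject) matrix or the random-effect matrix, and whether the subject effect stays in the model at the fallback.

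The SAP applies this model in one place, section 9.4: "CFB will be compared using the MMRM and ANCOVA methods as used for the primary endpoint for each item individually". The visits there are baseline and "Week 5, Week 9, Week 13 and Week 25", so there are four post-baseline visits. The questionnaire has five core and six modular items, hence 11 analyses.

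Protocol 9.4.3 and 9.4.4 also plan an MMRM for the primary endpoint, where the model with "treatment-by-visit interaction will be used as a sensitivity analysis". Neither section mentions a random subject effect or a covariance structure. SAP 7.2.3 does not carry that analysis forward.

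**The concern.** In an MMRM the unstructured residual matrix already describes all the within-subject covariance. A random intercept adds the same constant to every element of that matrix, so it contributes nothing the matrix cannot already represent. The optimiser then faces a flat direction in the likelihood, which may lead it to report non-convergence. Non-convergence is exactly the condition that sends the analysis to variance components.

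That makes the fallback matter. It moves in one step from the most flexible structure to one of the most restrictive, with nothing in between. If its assumptions are wrong, the standard errors at a given visit are wrong. If it amounts to independence, a subject's earlier scores no longer inform her missing later ones, and the inference loses the missing-at-random validity the section relies on. The choice between the two versions of the fallback would also be made while fitting, because the text does not settle it.

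**Working it through.** **Inputs.** From the documents: four post-baseline visits (SAP 9.4), 34 evaluable subjects per group and an SD of 2.0 for the dysmenorrhea NRS (SAP 1.4), two-sided 5% tests (SAP 7.1). No figure in either document is attached to the MMRM covariance, so there is no stated figure to reproduce. Within-subject correlations, the pattern of SDs over visits and the dropout mechanism are my assumptions.

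**Step 1: count the parameters, taking unstructured as the residual matrix.** The marginal covariance is V = R + τ²J, where R is unstructured, τ² is the random-intercept variance and J is the matrix of ones. With T visits, V has T(T+1)/2 distinct elements, while R and τ² together have T(T+1)/2 + 1 parameters.

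| T | Parameters | Rank |
|---|---|---|
| 2 | 4 | 3 |
| 3 | 7 | 6 |
| 4 | 11 | 10 |

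There is always exactly one too many. As an example, take T = 4, variance 4 and first-order autoregressive correlation 0.6. That V is reproduced exactly by τ² = 0 with R = V, and by τ² = 0.5 with R = V − 0.5J, which is still positive definite. Only the split is undetermined. V, and therefore the treatment contrasts, remain identified. Without the random effect there are 10 parameters and rank 10.

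**Step 2: the other reading.** If unstructured describes the random-effect matrix of a single subject intercept, it is one variance. The model is then identified, but with an independent equal-variance residual it is only compound symmetry, not an unstructured within-subject model.

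**Step 3: the fallback.** With the subject effect kept, variance components has two parameters (rank 2): V = σ²I + τ²J. Every visit has variance σ² + τ², and every pair of visits has correlation τ²/(σ² + τ²). With the subject effect dropped, all correlations are zero.

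**Step 4: unequal variances, complete data, two arms of 34.** Assume SDs of 1.5, 1.8, 2.1 and 2.4.

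- Variances: 2.25, 3.24, 4.41, 5.76. Mean: 15.66/4 = 3.915.
- Model SE of the last-visit difference: √(2 × 3.915/34) = 0.480.
- True SE: √(2 × 5.76/34) = 0.582.
- Ratio 0.480/0.582 = 0.824, so the effective critical value is 1.96 × 0.824 = 1.616 and the type I error is 2 × [1 − Φ(1.616)] = 0.106.

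A simulation of the same case with correlation 0.7 (1,500 runs) gave 0.113 for compound symmetry and for independence, and 0.052 with the correct unstructured matrix.

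Reverse the SDs so that they fall from 2.4 to 1.5. The true SE is √(2 × 2.25/34) = 0.364, the ratio is 0.480/0.364 = 1.319, the critical value is 2.585 and the type I error is 0.010.

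Only the ratios of the SDs matter here, so the result does not depend on the measurement scale.

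**Step 5: missing at random, equal variances.** Simulation with SD 2.0, autoregressive correlation, dropout in one arm that rises with the previous score, 22–24% missing at the last visit, 1,500 runs. Bias is in points, with SD 2.0.

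| Correlation | Compound symmetry: bias, type I error | Independence: bias, type I error |
|---|---|---|
| 0.3 | 0.04, 0.056 | −0.14, 0.061 |
| 0.5 | 0.08, 0.061 | −0.24, 0.071 |
| 0.7 | 0.06, 0.055 | −0.42, 0.117 |
| 0.9 | 0.02, 0.051 | −0.62, 0.177 |

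Under the unstructured matrix the bias is at most about 0.01 in size. Monte Carlo error is about 0.006 for a type I error near 0.05 and 0.015 for bias. With complete data and equal variances all three structures give identical estimates and SEs.

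**The case against.** The strongest reply is that little depends on this. The SAP's primary analysis is multiple imputation with ANCOVA (7.2.2), its sensitivity analysis is a variant of the same (7.2.3), and the secondary pain endpoints follow it (7.3). The MMRM serves only the exploratory EHP-5, which is also analysed by ANCOVA with last observation carried forward. This stands, and it sets the size of the point.

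A reader might infer that the treatment effect cannot be identified. The documents do not support that: only the split between intercept variance and residual matrix is undetermined, and only on the residual reading.

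A reader might infer that the fallback throws away the within-subject correlation. On the literal text it does not. The subject effect is part of the model and nothing removes it, so correlation is kept but forced to be constant. In Step 5 that version performs tolerably; its failure comes from unequal variances. Independence arises only if the subject effect is dropped as well.

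A reader might also infer that the fallback will usually become the real analysis. That is not shown. The redundancy can prevent convergence, but software may still converge on a flat likelihood, and the SAP names no other trigger.

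Finally, the dropout in Step 5 exceeds the 10% planned in SAP 1.4 and is arm-dependent by construction, so those biases are illustrations.

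**Conclusion.** The specification is defective on the usual residual reading and ambiguous on any reading. The defect is one redundant covariance parameter in every fit, followed by a single fallback whose meaning the SAP leaves open. Under compound symmetry, the last-visit type I error is about 0.11 with SDs assumed to rise from 1.5 to 2.4 and about 0.01 with them falling. Under independence there is also bias when dropout depends on earlier scores. These sizes rest on assumed SDs, correlations and dropout, since the documents give none for EHP-5, and they apply only if the fallback is reached.

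The reach is small: 11 exploratory item analyses in the current SAP. One might read the protocol as making the primary result rely on this model, but the SAP's primary and secondary pain analyses do not use it. If the MMRM sensitivity analysis in protocol 9.4.3–9.4.4 is run, SAP 7.1.3 is the only text that would define its covariance, and the point would then carry more weight. SAP section 10 does not list that analysis as dropped, though it compares against protocol version 6.1 while the protocol reviewed here is 6.0. This is a worthwhile minor correction.

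**What to change.** Rewrite the MMRM paragraph in SAP 7.1.3:

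- Delete subject as a random effect.
- State that the unstructured matrix is the residual within-subject matrix (the REPEATED statement in SAS), with Kenward-Roger degrees of freedom.
- Replace variance components with a pre-specified ordered list that allows unequal variances, for example heterogeneous Toeplitz, then heterogeneous AR(1), then heterogeneous compound symmetry, and take the first that converges. Other orders are defensible; what matters is fixing one in advance.
- If sandwich standard errors are chosen for a fallback fit, say that they replace Kenward-Roger there. They correct the standard errors but do not restore validity under missing at random when the working covariance is wrong, so they do not replace a flexible structure.

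The cost is one SAP paragraph and slightly more programming. No data collection or sample size changes.

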7.1.4 Multiple Comparisons/Multiplicity

Multiplicity adjustment will not be employed with respect to the multiple dose groups in this proof-of-concept study.

7.1.5 Interim Analyses

In addition to the ongoing safety data monitoring, two unblinded interim analysis (IA) of the efficacy data are planned after 60 subjects or 100 subjects completed Week 12 visits separately, or other IA requested by the sponsor. The objective of the interim analysis is to provide preliminary data, and no adjustment of significance level will be employed. The statistical hypotheses tests for the final analysis will be performed at the 0.05 level as described in Section 9.1. This interim analysis will be performed by an analysis team that is independent from the study team responsible for the study conduct and the final analysis. The TFLs performed for IA will be specified in a separate listing.

7.1.6 Examination of Subgroups

The uniformity of the treatment effect for the primary efficacy variable and NMPP will be examined for the following subgroup:

- Asian vs. Others (combined from the randomization strata of region: China for Asian, the USA and Europe for Others)

Summary tables will be provided by subgroup category. The treatment effects across the subgroups defined will be estimated for the mean change and percentage mean change of DYS and NMPP measured by NRS from Baseline to Week 12 on the PAS and using a similar approach as applied to the analysis for the primary efficacy endpoint. Since the randomization strata factor is used to define one of subgroups, the corresponding strata factor will not be included in the model.

The adjusted estimates of treatment mean differences (each HMI-115 treatment group vs. placebo) with SEs and 95% CIs will be provided as appropriate across the subgroups.

Summaries of the primary efficacy variable by treatment group and subgroups will be produced. No formal statistical analysis will be performed within subgroup.

[figure not shown]

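### The subgroup section sets out to examine whether the effect is uniform between China and the USA/Europe, but no planned output estimates the difference between the two effects

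*SAP*

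**What the plan says.** The aim is in the first line of SAP 7.1.6: "The uniformity of the treatment effect for the primary efficacy variable and NMPP will be examined". There is one subgroup factor, Asian versus Others, "combined from the randomization strata of region: China for Asian, the USA and Europe for Others".

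The planned output is by subgroup: "The adjusted estimates of treatment mean differences (each HMI-115 treatment group vs. placebo) with SEs and 95% CIs will be provided as appropriate across the" […]. It covers change and percentage change in DYS and NMPP from Baseline to Week 12, on the PAS, by an approach similar to the primary analysis. The region term is dropped: "the corresponding strata factor will not be included in the model". The section closes with "No formal statistical analysis will be performed within subgroup".

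Elsewhere, SAP 7.1.1 adjusts the primary model "by including region as a main effect term in the model" and offers a descriptive summary by center. Neither document contains a treatment-by-region or treatment-by-subgroup term, a between-subgroup difference, or a criterion for calling the effect uniform.

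**The concern.** The question and the output do not match. Whether an effect is uniform is answered by the difference between the Asian effect and the Others effect, with its uncertainty. The plan gives the two effects separately and leaves the comparison to the eye.

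There are 12 such comparisons: 2 endpoints × 2 scales (change and percentage change) × 3 doses. The common shortcut is to ask whether each interval excludes zero. With small subgroups that shortcut often gives one yes and one no when the true effect is the same in both. The table would also not show how large a real regional difference the data allow.

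**Working it through.** **Inputs from the documents.** SD 2.0 and 34 evaluable per arm (SAP 1.4); 1.4 points as the between-group difference with 80% power (Protocol 9.2); two-sided 5% level (SAP 7.1).

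**Assumptions.** The Asian:Others split is not stated, so it is varied from 50:50 to 90:10. The PAS is the surgically diagnosed part of the FAS (SAP 3.3) and its size is not stated, so 34 per arm is the overall planning figure, not a PAS figure. SD 2.0 is used as the residual SD.

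**1. The plan's own figures.**
- Paired t-test, 1 point, n = 34: noncentrality 1/(2/√34) = 2.92, 33 df, power 80.8%. Reproduced.
- Two-sample t-test, 1.4 points, n = 34 per arm: noncentrality 1.4/(2√(2/34)) = 2.89, 66 df, power 81.2%. Reproduced.

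**2. One subgroup at an even split.** With 17 per arm, the SE of a dose-versus-placebo difference is 2√(2/17) = 0.686. The noncentrality is 1.4/0.686 = 2.04 on 32 df, so the 95% CI excludes zero with probability 50.8%.

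**3. Discordance under a uniform effect.** Here discordant means that exactly one of the two subgroup CIs excludes zero. The subgroups contain different subjects, so the probability is p_A(1 − p_O) + p_O(1 − p_A).
- 1.4 points, 50:50: 2 × 0.508 × 0.492 = 50%.
- 1.0 point, 50:50 (p = 0.293): 2 × 0.293 × 0.707 = 41%.
- 1.4 points, 80:20 (27.2 and 6.8 per arm, p = 0.717 and 0.220): 0.717 × 0.780 + 0.220 × 0.283 = 62%.
- 2.0 points, 50:50 (p = 0.807): 2 × 0.807 × 0.193 = 31%.
- No effect: 2 × 0.05 × 0.95 = about 10%.

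| Split (34 per arm) | 1.0 point | 1.4 points | 2.0 points |
|---|---|---|---|
| 50:50 | 41% | 50% | 31% |
| 70:30 | 43% | 56% | 44% |
| 80:20 | 46% | 62% | 60% |
| 90:10 | 49% | 71% | 80% |

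A simulation with four arms, pooled variance and shared placebo gives 50%, 56% and 62% at 1.4 points for the first three splits. With a smaller PAS of 24 per arm, effects of 1.0–1.4 points and splits up to 80:20 give 34–54%.

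**4. A stricter meaning of discordant.** If it means estimates of opposite sign, the probability is Φ(δ/SE_A)[1 − Φ(δ/SE_O)] plus the reverse. At 1.4 points this is 4% (50:50), 6% (70:30) and 10% (80:20). At 1.0 point it is 13% (50:50) to 20% (80:20).

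**5. The missing quantity.** The SE of the Asian-minus-Others difference in the dose-versus-placebo effect is 2√(2/n_A + 2/n_O), where n is per arm within the subgroup. Half-width is 1.96 × SE; the difference detectable with 80% power is 2.80 × SE.

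| Split | SE | 95% CI half-width | Detectable |
|---|---|---|---|
| 50:50 | 0.97 | 1.9 | 2.7 |
| 70:30 | 1.06 | 2.1 | 3.0 |
| 80:20 | 1.21 | 2.4 | 3.4 |

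For a truly uniform effect, the 95% CI for this difference excludes zero in 5% of trials per dose.

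**The case against.** Four points can be made for the plan.

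- *The misreading is not planned.* The SAP disclaims formal analysis within subgroup, and no significance statement per subgroup is promised. This stands: the discordance rates describe what a reader may do with the table. But the disclaimer is about inference within a subgroup. It does not supply the comparison between subgroups that the section announces.
- *The difference can be derived.* If the subgroups are analysed separately, it is one subtraction, with SE about √(SE_A² + SE_O²); at 17/17 that is √(0.686² + 0.686²) = 0.97. This largely stands. The gap is a derived row, not missing data.
- *The contrast is imprecise.* A half-width of 1.9 points or more exceeds the 1.4-point effect, and this is one descriptive subgroup in a proof-of-concept trial. This stands as a reason to label it descriptive. It is not a reason to leave readers with two wide intervals and no statement of how little they say about uniformity.
- *The rates depend on assumptions.* This stands. A reader might infer that a uniform effect will look discordant about half the time as a general fact. The 50% needs a 1.4-point effect, an even split, 34 per arm, a single dose and the CI-excludes-zero reading. Protocol 9.2 also says the sample size was not based on power against placebo.

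**Conclusion.** The mismatch is confirmed: SAP 7.1.6 states a question about uniformity and plans no estimate that answers it. It is a minor point with a cheap remedy, and the primary result does not depend on it.

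For a given dose, a truly uniform effect would look discordant in roughly 41–62% of trials if the two CIs are compared by whether each excludes zero. This rests on a true effect of 1.0–1.4 points, SD 2.0, 34 per arm and splits from 50:50 to 80:20. Outside those conditions the rate moves widely, and the actual split and PAS size are unknown.

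Two stronger readings are tempting but not supported:
- A reader might infer that discordance in at least one of the three doses is nearly certain. The simulated rates are 83% at 50:50 and 86% at 70:30, but only if every dose has a true effect of 1.4 points. Protocol 4.3.2 proposes 60 mg as the minimum and 240 mg as the maximum effective dose, so equal effects are not the design's expectation.
- A reader might infer that the subgroup result will steer regional planning of later studies. The documents speak of choosing a dose for pivotal studies (Protocol 2.1) and of interim data for later development (Protocol 9.5). Neither mentions regional planning.

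**What to change.** In SAP 7.1.6, add for each dose the Asian-minus-Others difference in the dose-versus-placebo effect with its 95% CI, labelled descriptive.

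- **Analysis model.** Fit one model on the PAS with treatment, region at three levels, baseline and treatment-by-subgroup interaction. Region at three levels already carries the subgroup main effect, and it keeps the USA-versus-Europe adjustment that dropping region removes within Others.
- **Imputation models.** The models in SAP 7.2.2 have treatment and region as main effects only. Run unchanged on the whole PAS, they would impute values with no built-in treatment-by-region interaction and pull the contrast toward zero. As an illustration, if 10% of values were imputed in every cell, a true difference d would shrink to as little as 0.9 × d + 0.1 × 0 = 0.9d. Add the treatment-by-subgroup term to both the missing-at-random and the missing-not-at-random steps, or impute within subgroup. The first may be more stable if one subgroup is small.
- **Interpretation.** State that uniformity is judged from this difference and its interval, not from whether each subgroup CI excludes zero.

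The cost is one extra model per endpoint, one extra term in the imputation code and one row per dose in the table shell. The downside is the wide interval (see the last table in the working). It can neither establish nor exclude a moderate regional difference, and the report should say so. If the sponsor prefers not to add the contrast, the section should no longer be described as an examination of uniformity.
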